10.2 Blinding, Randomization and Stratification

This is an open-label study.

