11.3 Discontinuation Criteria

A subject may be discontinued from the study or study drug for any of the following reasons:

- Withdrawal of consent by the subject and/or subject's legal guardian;
- Investigator or Sponsor decision that withdrawal is in the subject's best interest;
- Deterioration of the clinical condition or delayed response requiring, in opinion of the Investigator, alternative therapy;
- Occurrence of an AE that, in the opinion of the Investigator, warrants discontinuation of the subject from the study drug;
- Pregnancy;
- Lost to follow up (every attempt should be made to contact the subject).

The reason for a subject's discontinuation of treatment or withdrawal from the study will be clearly documented in the source documents and on the electronic case report form (eCRF).

For VVC subjects, all TOC procedures should be performed for subjects who discontinue from the study before the TOC visit, and all 25-Day FU procedures should be performed for subjects who discontinue from the study after the TOC visit but before the 25-Day FU visit.

For all other fungal diseases, at the time of discontinuation, all EOT procedures should be performed for subjects who discontinue from treatment on or before the EOT visit and the 6-Week FU visit should also be completed. All 6-Week FU procedures should be performed for subjects who discontinue from the study after the EOT visit and on or before the 6-Week FU visit. All follow up visits should be completed for discontinued subjects regardless of need for additional antifungal therapy.

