18.2 Analysis Populations

The study populations to be used in the analyses are defined as follows:

- Intent-to-Treat Population: The intent-to-treat (ITT) population will include all subjects who are enrolled in the study and receive at least 1 dose of study drug.
- MITT: the Myco-ITT population will include all ITT subjects with confirmed pathogens and who also had all necessary cultures or mycology tests to estimate mycological response.

- **Per-Protocol Population:** The per-protocol (PP) population will include all ITT subjects who receive enough study drug (ibrexafungerp) to enable clinical efficacy judgement as determined by the DRC, who have an EOT (TOC for VVC, CMC, CPA and ABPA) assessment and who have no major protocol violations.
- **Safety Population:** The safety population will include all subjects who receive at least one dose of study medication and have at least one safety assessment post Baseline.
- **Pharmacokinetic Population:** The PK population will include all enrolled subjects who provide at least one PK sample and no deviations significant enough to affect the interpretability of PK data.

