### **3.2 Analysis Populations**

The analysis populations to be used in the analysis are defined as follows:

**Intent-to-Treat Population:** The intent-to-treat (ITT) population will include all subjects who are enrolled in the study and receive at least 1 dose of study drug.

**Myco-ITT:** the Myco-ITT population will include all ITT subjects with confirmed pathogens and who also had all necessary cultures or mycology tests to estimate mycological response.

**Per-Protocol Population:** The per-protocol (PP) population will include all ITT subjects who received enough study drug (ibrexafungerp) to enable clinical efficacy judgement as determined by the DRC, who have an EOT (TOC for VVC, CMC, CPA and ABPA as applicable) assessment and who have no major protocol violations that could impact the assessment of efficacy (Refer to Section 7).

**Safety Population:** The safety population will include all subjects who receive at least one dose of study medication and have at least one safety assessment post Baseline.

**Pharmacokinetic Population:** The pharmacokinetic (PK) population will include all enrolled subjects who provide at least one PK sample and no deviations significant enough to affect the interpretability of PK data.

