### **4.2 Protocol Deviations**

The investigator may not deviate from the protocol without a formal protocol amendment having been established and approved by an appropriate IRB, except when necessary to eliminate immediate hazards to the subject or when the change(s) involve(s) only logistical or administrative aspects of the study.

Major protocol deviations will be defined in the significant protocol deviations rules document. Each significant deviation will be assigned a rule number. As the study is ongoing, additional significant protocol deviations can also be spontaneously identified or defined by the sponsor and/or the project team during the regularly planned study deviation review meetings and the significant protocol deviations rules document can be updated.

All protocol deviations will be reviewed and assessed as to significance prior to the database lock. The list of protocol deviations (major or minor) that are additionally considered major clinically relevant for the purposes of analysis will also be identified and documented prior to the database lock.

All major protocol deviations will be summarized for all enrolled subjects. Major protocol deviations will also be presented in a listing.

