## 7. EFFICACY

The primary efficacy and secondary efficacy endpoints will be performed on the ITT, Myco-ITT and PP populations. The ITT analyses will be considered primary and the Myco-ITT and PP analysis will be considered supportive of the primary analyses on the ITT population.

The primary efficacy endpoint of the study is the percentage of subjects who achieve Global Response at TOC for VVC (Day 17), CMC (EOT or Day 84), CPA (EOT or Day 90) and ABPA (EOT or Day 90) (whichever comes first) and at EOT for all other diseases, as determined by the DRC. The primary efficacy endpoint will also be summarized by disease category and reason for enrollment separately. Secondary efficacy endpoints include the percentage of subjects who achieve Global Response, Clinical Response and Mycological Response by pathogen, fungal disease, disease category, and reason for enrollment at several time points as assessed by the DRC and by the Investigator. The following enrollment categories, as determined by the DRC unless stated otherwise, will be utilized: Refractory, Intolerant, Resistant (includes step-down cases), Toxicities, Relapse, Step-Down (as determined by PI). Each subject's enrollment reason will be validated by the DRC. The percentage of subjects with a recurrence, ACM and time to death will also be assessed.

Efficacy outcomes will be based on definitions captured in [Table 5](#) and [Table 6](#). Criteria for the DRC assessment of response will be further detailed in the DRC Charter. Criteria for the Investigator is outlined in [Section 7.2](#).

Efficacy evaluations will consist of clinical evaluations of the signs and symptoms of infection, mycological testing (including, but not limited to, fungal culture, KOH and other fungal stains, and T2 testing), imaging (e.g., CT, MRI, X-Ray or ultrasound) and serological testing (including, among others,  $\beta$ -D-glucan levels, GM and fungal antibody titers) as applicable for each fungal disease. Additional procedures (esophagoscopy, spirometry, St. George's Respiratory Questionnaire [SGRQ], 6-Minute Walk Test and Medical Research Council [MRC] Dyspnea Scale) will be conducted for selected fungal diseases.

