Other secondary efficacy assessments will include recurrence and survival. Recurrence will be evaluated at the 6-Week FU visit after EOT for all subjects, except VVC subjects, who will be assessed for recurrence at the 25-Day FU visit. Survival status data was collected at Day 42 and Day 84. A subject's date of death will be used to determine their survival status at Day 30. Survival will be determined at Day 30 for IC/Candidemia and at Day 42 for all subjects. Additional disease-specific efficacy endpoints will be evaluated for selected fungal diseases at additional time points ([Table 7](#)).

A determination of the potential impact of protocol deviations on the efficacy-related outcomes was done by the sponsor for the purpose of defining the PPP:

- Unapproved co-administration of other systemic or topical (in case of mucosal infections) antifungal for  $\geq 10\%$  of the ibrexafungerp treatment duration or for longer than 3 days (whichever is shorter) was considered a protocol deviation warranting exclusion from the PPP.
- An EOT visit that occurred  $> 2$  weeks after last dose of ibrexafungerp for non-VVC subjects was considered a protocol deviation warranting exclusion from the PPP.

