## 7.1 Primary Endpoint

The primary efficacy objective is to evaluate the efficacy of ibrexafungerp in the treatment of severe fungal diseases by a Data Review Committee (DRC) at the primary timepoint for the fungal disease (as defined in [Table 5](#)). The primary efficacy endpoint of the study is the percentage of subjects who achieve Global Response (as defined in [Table 6](#)) at TOC (Day 17) for VVC, CMC (EOT or Day 84), CPA (EOT or Day 90) and ABPA (EOT or Day 90) (whichever comes first) and at EOT for all other diseases, as determined by the DRC. The analysis criteria will be based on EORTC-MSG Consensus Criteria for all diseases except ABPA, CPA and VVC.

Table 6 EORTC-MSG General Criteria for Global Responses to Antifungal Therapy with adaptations a and b

Global Response	Outcome Criteria
Success	Complete Response: Survival within the prespecified period of observation, resolution of all attributable symptoms and signs of disease and radiological abnormalities, and mycological evidence of eradication of disease a For subjects who were enrolled for step-down therapy and who were asymptomatic at baseline: no new symptoms or signs suggestive of disease and no new positive cultures.
	Partial Response: Survival within a prespecified period of observation, improvement in attributable symptoms and signs of disease and radiological abnormalities, and evidence of clearance of cultures or reduction of fungal burden, and no new positive cultures, as assessed by a quantitative and validated laboratory marker
Failure	Stable Response: Survival within a prespecified period of observation and minor or no improvement in fungal disease, but no evidence of progression, as determined on the basis of a composite of clinical, radiological and mycological criteria.
	Progression of Fungal Disease: Evidence of progressive fungal disease based on a composite of clinical, radiological and mycological criteria
	Death: Death during the prespecified period of evaluation, regardless of attribution
bNot Evaluable	Outcome cannot be assessed due to missing data

aDefinition added in Amendment 3 for subjects enrolled for step-down therapy and asymptomatic at baseline. DRC adjudications followed this definition for all subjects, PI adjudication followed this definition for subjects enrolled after Amendment 3.

bCategory added for non-evaluable subjects due to missing data

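### The DRC decides who had enough drug for the per-protocol set and also scores the outcome, with no stated minimum, order or masking, so the supportive PP rate can be raised by selective exclusion

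*SAP*

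**What the plan says.** SAP 3.2 defines the PP set as ITT subjects "who received enough study drug (ibrexafungerp) to enable clinical efficacy judgement as determined by the DRC", who also have an EOT assessment (TOC for four diseases) and no major violation that could affect efficacy. Protocol 18.2 has the same exposure clause: "who receive enough study drug (ibrexafungerp) to enable clinical efficacy judgement as determined by the DRC". Neither gives a number of days or doses.

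The DRC also scores the primary endpoint. SAP 7.1 sets Global Response at TOC for VVC, CMC, CPA and ABPA and "at EOT for all other diseases, as determined by the DRC". Protocol 10.2 states: "This is an open-label study".

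The one timing rule nearby is in SAP 4.2: "All protocol deviations will be reviewed and assessed as to significance prior to the database lock". It covers deviations, not exposure, and for the PP set those are judged by a different party: "A determination of the potential impact of protocol deviations on the efficacy-related outcomes was done by the sponsor" (SAP 7).

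On the role of the PP set, SAP 7 says "the Myco-ITT and PP analysis will be considered supportive of the primary analyses on the ITT population".

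**The concern.** Whether drug exposure was sufficient to judge efficacy is hard to answer without thinking about what happened to the subject. The committee that answers it is also the one that knows the outcome.

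Short exposure and failure are linked by design. Protocol 11.3 lists, as a reason to stop, "Deterioration of the clinical condition or delayed response requiring, in opinion of the Investigator, alternative therapy". The discretion therefore operates where failures are likely to be found. A subject who worsens after a few days may be judged under-treated, while one who clears in the same few days may be judged adequately treated.

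If that happens, the PP rate rises with no change in drug effect, and apparent agreement between PP and ITT reassures less than it seems to. There is no control arm in which similar exclusions could offset the shift, and Protocol 18.4.3 plans to set the response rates beside external data. The other PP exclusions in SAP 7 are numeric (unapproved antifungal use for at least 10% of treatment or more than 3 days; an EOT visit more than 2 weeks after the last dose). Exposure is the criterion left without a number.

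**Working it through.** The plan states no PP size, PP rate or expected response, so there is no planned figure to reproduce. What follows is an illustration.

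**Inputs**
- N = 220: planned enrolment (Protocol 18.1, SAP 3.1).
- ITT response 55%: assumed, taken from the preliminary DRC review in Protocol 7.1 (11 of 20). Responders R = 0.55 × 220 = 121.
- d = 22 subjects with short exposure (10% of N): assumed.
- s = 4 to 9 responders among those 22: assumed.
- 95% intervals: Clopper-Pearson, as in SAP 7.1.1.

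**Formulas**
- ITT rate = R / N
- Fixed minimum, all short courses excluded: (R − s) / (N − d)
- Selective exclusion, only the failures among them excluded: R / (N − (d − s))
- Selective part = selective rate − fixed-minimum rate

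**Reference values**
- ITT: 121/220 = 55.0% (48.2 to 61.7).
- If 22 are excluded without regard to outcome: 109/198 = 55.1%, essentially no change.

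**Splitting the rise**

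| Responders among 22 short courses | Fixed minimum | Selective exclusion | Rise over ITT from a fixed minimum | Selective part |
|---|---|---|---|---|
| 4 | 117/198 = 59.1% | 121/202 = 59.9% | 4.1 points | 0.8 points |
| 9 | 112/198 = 56.6% | 121/207 = 58.5% | 1.6 points | 1.9 points |

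**The extreme case.** If every excluded subject is a failure, 11 exclusions give 121/209 = 57.9% and 22 give 121/198 = 61.1%. These are larger rises (2.9 and 6.1 points), but they do not measure discretion. With s = 0 the two formulas coincide: a programmed minimum that caught the same 22 failures would also give 121/198 = 61.1%.

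**Small cells.** SAP 7.1.1 reports PP results by disease, enrollment category and pathogen, with intervals from 5 subjects upward. In a hypothetical cell of 10 with 5 responders, dropping two failures moves 5/10 = 50% to 5/8 = 62.5%.

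**The case against.** The case on the other side has real weight.

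- **The PP set is only supportive.** ITT is primary and keeps every dosed subject, and the study is exploratory. This stands and limits the seriousness of the point.
- **The criterion asks whether efficacy can be judged, not whether the subject responded.** SAP Table 6 makes death and progression failures, so such subjects do have a judgeable outcome. The protocol also calls the DRC independent. Both points make selective exclusion less likely, but neither masks the committee or fixes an order.
- **The DRC Charter may settle it.** It is to hold detailed criteria and cannot be checked here. The point is therefore confined to what the protocol and SAP state.
- **Other clauses remove subjects too.** Someone who dies early without an EOT or TOC assessment can leave the PP set on that ground, whatever the DRC thinks of exposure.
- **A minimum chosen now could be tuned.** SAP Table 6 (footnote) and 7.2.3 describe DRC adjudication in the past tense, so a threshold invented today could be set with results in view. This stands and shapes the fix.

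A reader might infer that the PP rate is in fact biased upward, or that any excess of PP over ITT is the DRC's doing. The documents support neither. Nothing in them shows that selective exclusion occurred, and failures that stop early would raise the PP rate under a neutral rule as well.

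**Conclusion.** The gap is real on the text: one committee makes both decisions, with no numeric minimum and no stated order or masking, in a study where outcomes are visible. The rule permits exclusion that depends on outcome and can raise the supportive PP rate. It cannot alter the primary ITT result.

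The direction is certain only if short-exposure failures are dropped more readily than responders with like exposure. The size is unknown. Under the assumptions above, the part due to selective discretion is about 0.8 to 1.9 points overall, small beside an ITT interval running from 48.2% to 61.7%, though small subgroups could shift more. It is worth correcting because the correction is cheap and the PP set is there to corroborate ITT.

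**What to change.** 1. For any subject not yet adjudicated, make the exposure decision from dosing data only, and record and lock it before the DRC adjudicates outcome. If the Charter already requires this, cite it in SAP 3.2.
2. For subjects already adjudicated, do not choose a new minimum now. As a PP sensitivity analysis, apply by program to all subjects an exposure minimum that was set without reference to outcomes. The superseded Amendment 2 PP definition, recorded in the protocol's revision history (at least 5 days of study drug, 1 day for VVC), is a candidate. It dates from 2019, but the sponsor should confirm that it was not informed by early results. SAP 6.2.1 already derives treatment duration and cumulative doses.
3. State in SAP 3.2 that death or adjudicated failure on or before EOT/TOC satisfies the assessment requirement, so that early failures who meet the exposure rule stay in.
4. Tabulate PP exclusions by reason and by ITT Global Response. SAP 4.1 already counts subjects in each population, but not by outcome.

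The cost is one derived variable and one table, plus a two-step DRC record for any remaining cases. A fixed minimum may exclude a few informative short courses. It also leaves in place the rise caused by failures stopping early, so PP should still be read beside ITT.

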### **3.3 General Handling of Missing Data**

For incomplete dates related to concomitant medications, the dates will be imputed as follows:

If the incomplete date is a start/onset date:

- (1) if the month and year are present, then the first day of the month will be used for day.
- (2) if only the year is present, then the first day of January will be used for month and day.

If the incomplete date is an end date:

- (1) if the month and year are present, then the last day of the month will be used for day.
- (2) if only the year is present, then the last day of December will be used for month and day. If the reported year is the same as the informed consent year, then the informed consent date will be used.

Dates that are completely missing will not be imputed.

Baseline values that are missing will not be imputed. Subjects who have missing subgroup values will not be included in that particular subgroup analyses.

If efficacy data are missing and the subject has not been deemed a success or failure the outcome will be categorized as unknown.

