#### 6.1.1 Prior Medications

Prior medications are defined as medications taken and stopped prior to the first dose of study drug. The number and percentage of subjects who took prior medications will be presented by WHO therapeutic drug class and generic drug name.

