#### 6.1.2 Concomitant Medications

Concomitant medications are defined as medications that are ongoing at or started after the first dose of study drug and started on or before the FU visit date, regardless of whether the stop date is missing. Medications with a stop date after the first dose of study drug are also considered concomitant medications. Medications with incomplete or missing dates will be handled as detailed in [Section 3.3](#). A summary showing the number and percentage of subjects who took concomitant medications will be presented by WHO therapeutic drug class and generic drug name.

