### 8.1 Adverse Events

All AE summaries will be restricted to treatment-emergent AEs (TEAEs) only. A TEAE is defined as any event not present before exposure to study drug or any event already present that worsens in either intensity or frequency after exposure to study drug.

For the purpose of inclusion in TEAE tables, incomplete AE start and end dates will be imputed as follows:

Missing onset dates (where UK and UNK indicate unknown or missing day and month respectively):

- UK-MMM-YYYY: If the month and year are different from the month and year of the date of first dose, assume 01-MMM-YYYY. If the month and year are the same as the month and year for the date of first dose, and the end date (after any imputation) is on or after the date of first dose, then assume the date of first dose. If the month and year are the same as the date of first dose, and the end date (after any imputation) is prior to the date of first dose, then assume the end date for the start date.
- DD-UNK-YYYY/UK-UNK-YYYY: If the year is different from the year of the date of first dose, assume 01-JAN-YYYY of the collected year. If the year is the same as the date of first dose year, and the end date (after any imputation) is on or after the date of first dose, then assume the date of first dose. If the year is the same as the date of first dose, and the end date (after any imputation) is prior to the date of first dose, then assume the end date for the start date.

Missing end dates (where UK and UNK indicate unknown or missing day and month respectively):

- UK-MMM-YYYY: Assume the last day of the month;
- DD-UNK-YYYY/UK-UNK-YYYY: Assume 31-DEC-YYYY.

All adverse events will be classified by SOC and PT according to the Medical Dictionary for Regulatory Activities (MedDRA, March 2023 Version 26.0). An overview summary of the number and percentage of subjects with any TEAE, serious TEAE, treatment-related TEAE,

treatment-related serious TEAE, TEAE leading to study treatment discontinuation, TEAE leading to study discontinuation, and AE leading to death will be provided.

All AEs will be presented in a listing.

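### Setting year-only medication stop dates in the consent year to the consent date can class on-treatment drugs as prior, shrink their overlap to 0–1 day, and put stop before start

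*SAP*

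**What the plan says.** SAP Section 3.3 gives the rules for incomplete medication dates.

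- Start dates: "if the month and year are present, then the first day of the month will be used for day", and "if only the year is present, then the first day of January will be used for month and day".
- Stop dates: a month-and-year date goes to the last day of that month. For a year-only date, "if only the year is present, then the last day of December will be used for month and day". The next sentence overrides this: "If the reported year is the same as the informed consent year, then the informed consent date will be used".
- Dates that are wholly missing are not imputed.

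Section 6.1.1 states: "Prior medications are defined as medications taken and stopped prior to the first dose of study drug". Section 6.1.2 states: "Concomitant medications are defined as medications that are ongoing at or started after the first dose of study drug". It adds that a stop date after first dose also makes a drug concomitant, that a missing stop date does not prevent this, and that incomplete dates follow Section 3.3.

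Protocol Section 14.1.1 requires consent before any screening evaluation. Protocol Table 3 and SAP Table 1 put screening at Days -1 [-3] and let it share a date with Day 1.

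Antifungal use after first dose matters in two further places. SAP Section 7 excludes from the per-protocol population "Unapproved co-administration of other systemic or topical (in case of mucosal infections) antifungal for" at least 10% of the ibrexafungerp treatment duration or longer than 3 days, whichever is shorter. SAP Table 7 counts completion of treatment in acute invasive candidiasis/candidemia only where no other antifungal was used.

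**The concern.** The consent date cannot fall after first dose, so the exception gives every year-only stop in the consent year a value on or before Day 1, even for a drug known to have been taken during treatment. Nothing in Section 3.3 checks that the imputed stop is on or after the start.

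The exception also runs against the rest of the section, which imputes stops late. A drug ongoing at first dose with no stop date can remain concomitant. If the year of stopping is known, the same drug can become prior, so more information gives the less cautious classification.

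The prior/concomitant boundary is a busy one in this trial, because many subjects enter after standard antifungal treatment. At stake are the accuracy of the medication tables and, if imputed dates were used there, the two decisions that depend on other antifungal use.

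**Working it through.** The plan gives no figure to reproduce, so the check applies its rules literally to constructed cases.

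**Inputs from the documents.** The Section 3.3 start and stop rules; prior if stop < first dose; concomitant if start is on or after first dose, or stop > first dose; consent ≤ first dose.

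**Assumptions.** Consent on 1 March. First dose 0, 1 or 3 days later. Treatment lasts 90 days. An antifungal truly stops on Day 60, with only the year recorded. Its start is before Day 1, on Day 10 or on Day 40, recorded in full, as month and year, or as year only. That gives 6 start patterns × 3 lags = 18 cases.

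**Formula.** Overlap in days = min(stop, end of treatment) − max(start, first dose) + 1, not below 0. True overlap is 60 days for a start before Day 1, 60 − 10 + 1 = 51 for Day 10, and 60 − 40 + 1 = 21 for Day 40.

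**Results.** The imputed stop is 1 March in every case.

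| Start, as recorded | Consent 1 or 3 days before dosing | Consent on dosing date | True overlap | Overlap under the rule (consent earlier / same day) |
|---|---|---|---|---|
| Before Day 1, full | prior only | neither by stop date | 60 | 0 / 1 |
| Before Day 1, year only | prior only | neither by stop date | 60 | 0 / 1 |
| Day 10, full | both; stop before start | concomitant; stop before start | 51 | 0 / 0 |
| Day 10, month and year | prior only | concomitant by start | 51 | 0 / 1 |
| Day 10, year only | prior only | neither by stop date | 51 | 0 / 1 |
| Day 40, month and year | both; stop before start | concomitant; stop before start | 21 | 0 / 0 |

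- Consent before dosing (12 cases): all 12 meet the prior definition. Eight are prior only. Four also meet the concomitant definition, with stop before start. For example, with first dose on 2 March, a Day 10 start is 11 March and the imputed stop is 1 March.
- Consent on the dosing date (6 cases): none is prior. Three are concomitant by start date, and two of these have stop before start. The other three stop exactly on Day 1, so neither stop-date test captures them, unless a drug stopping that day is read as ongoing at first dose.

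**Against the per-protocol threshold.** For 90 days of treatment, 10% is 9 days, so the shorter limit, more than 3 days, governs. If imputed dates were used, an overlap of 0–1 day would not trigger exclusion, whereas the true 21–60 days would, if unapproved.

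**Reach of the exception.** If consent is spread evenly over the year (an assumption), a stop on Day d falls in the consent year with probability of about 1 − d/365: 96% at Day 14, 88% at Day 42, 75% at Day 90 and 51% at Day 180. So most year-only on-study stops would meet the exception rather than the 31 December rule. This says nothing about how many year-only stops exist.

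**The case against.** Five points can be made for the plan.

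1. *Few records.* SAP Section 6.1 asks for start and stop times of concomitant medications taken during antifungal therapy. Year-only dates are more plausible for pre-enrolment history, where a stop at consent is a fair approximation. This stands as a limit on size. It does not excuse an interval that ends before it begins.

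2. *Not every record moves to prior.* A reader might infer that all affected drugs are misclassified in one direction. They are not: same-day consent and dosing produces no prior drug, and a drug whose imputed start is after first dose stays concomitant.

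3. *No shown effect on efficacy.* A reader might infer that the per-protocol and completion results look better than they should. The documents do not support that. SAP Section 7 says the sponsor determined the impact of deviations, and whether use was unapproved calls for case review. Section 7.2.2 has the disease-specific endpoints assessed by the DRC and/or investigator. Nothing says that either used imputed dates. Keeping a subject in the per-protocol set could also lower its response rate, if that subject failed. The primary analysis is DRC-determined Global Response in the ITT population, and no effect on it is shown.

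4. *Different purposes.* The adverse-event rule for a year-only end date, "Assume 31-DEC-YYYY", serves inclusion in treatment-emergent tables. It shows a different convention in the same SAP, not a contradiction. The case rests on Sections 3.3 and 6.1 alone.

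5. *The opposite rule errs too.* Late imputation counts some truly prior antifungals as concomitant. This is correct, and it shapes the fix.

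**Conclusion.** The rule is wrong as written and should be changed. In the cases where consent precedes dosing, it makes a drug that was taken into treatment prior only, or both prior and concomitant with an impossible interval. Where the two dates coincide, it leaves 0–1 day of overlap. The true overlap in the constructed cases was 21–60 days.

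The direct effect is on the prior and concomitant medication summaries and on any overlap computed from imputed dates. An effect on the per-protocol exclusion or the acute invasive candidiasis completion endpoint is possible but not shown. The gap between the two stop-date conventions can be long (1 March to 31 December is 305 days), but that is a distance between imputed dates, not an estimate of bias.

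The conclusion rests on the wording of Sections 3.3, 6.1.1 and 6.1.2 and on consent being no later than first dose. The overlap figures also rest on the assumed dates. The number of affected records is unknown and may be small.

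**What to change.** In SAP Section 3.3:

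- Delete the consent-year sentence.
- Impute a year-only stop date to the earlier of 31 December of that year and the last study contact, and never before the recorded or imputed start.
- Class a drug as concomitant when overlap with study drug cannot be excluded.

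In SAP Section 7 and Table 7, state that per-protocol exclusions and the requirement of no other antifungal use rest on reported dates, or on case review of flagged antifungal records, and not on imputed stop dates alone. State also which dates were used for the per-protocol determination already made.

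Applied to the 18 cases, with last contact taken as the 6-week follow-up, the new imputation makes all 18 concomitant, none prior and none with stop before start. Overlap becomes 59–90 days against a true 21–60, so it over-counts. That is tolerable in a medication table but not in an exclusion decision, which is why the second change is needed.

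The cost is a short SAP edit, minor programming and review of the flagged antifungal records. Some truly prior drugs will appear as concomitant in the tables; a footnote giving the number of imputed stop dates would let the reader judge how many.
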